11.2.2. Serious Adverse Event Reporting

The investigator shall report any serious adverse event (SAE) to the lead unit within 16 hours of becoming aware of it (Contact: [name], [contact]; [contact]) and to the Chinese Ethics Committee for Version 2.0

Release date: July 23, 2024

Registered Clinical Trials within 24 hours.

11.3. Prediction and Countermeasures of Adverse Events

All adverse events (AEs) that occur during the trial must be recorded truthfully in the AE form. Investigators should provide targeted treatment for AEs and conduct follow-up visits until the symptoms disappear or stabilize. For cases of serious adverse events (SAEs), investigators should immediately take necessary treatment measures upon learning of them to protect the safety of patients. Common AEs that may occur during interventional procedures include, but are not limited to:

1) Thromboembolic events

Possible causes include inadequate anticoagulation or incomplete anticoagulation, insufficient antiplatelet aggregation therapy or aspirin resistance, and the absence of continuous perfusion in the coaxial system. Reasonable and standardized anticoagulation and antiplatelet aggregation should be performed. If embolism occurs in important blood vessels, it should be managed by a professional doctor based on the patient's condition.

2) Cerebrovascular spasm

Cerebrovascular spasm can be caused by subarachnoid hemorrhage or irritation from intravascular catheters or guidewires. If cerebrovascular spasm occurs, symptomatic treatment should be provided by a professional doctor based on the patient's condition.

3) Acute occlusion

Possible causes include endothelial injury, platelet aggregation, and thrombosis, which usually occur within 30 minutes after balloon angioplasty or are related to endothelial avulsion.

Preventive measures: Antiplatelet agents such as aspirin or clopidogrel can effectively reduce acute thrombosis events.

Treatment measures: In case of acute occlusion, reasonable treatment should be immediately provided based on the cause of the occlusion.

4) Thrombosis and plaque dislodgment

These are mainly caused by the crushing and dislodgment of plaques during stent deployment or balloon dilation, and sometimes also due to thrombosis induced by catheters or guidewires. The use of cerebral protection devices and intraoperative anticoagulation are basic measures to prevent such events.

5) Vascular rupture

This type of complication can directly lead to patient death. When performing stent angioplasty in certain areas, it is advisable to choose an inner stent that is slightly smaller than the diameter of the target vessel. In case of vascular rupture, immediate symptomatic treatment should be provided by a professional doctor.

6) Cerebral hyperperfusion syndrome

In cases of large vessel occlusive disease, the regulatory capacity of distal vessels decreases due to long-term ischemia. Sudden recanalization of the occluded vessel significantly increases blood flow, and the distal vessels, especially the cortical arteries, cannot immediately adapt to this sudden increase in blood flow, leading to passive dilation and consequently, cerebral hyperperfusion syndrome. The main clinical manifestations are headache, head distension, nausea, vomiting, epilepsy, consciousness disturbance, and severe patients can have

intracranial hemorrhage.

The possibility of occurrence should be fully recognized before surgery, and blood pressure should be appropriately lowered during and after the procedure. If cerebral hyperperfusion syndrome occurs after surgery, symptomatic treatment (such as analgesics, antiepileptic drugs, etc.), dehydrating agents to reduce intracranial pressure, and surgical management of cerebral hemorrhage can be provided based on the patient's actual condition.

12. Statistical Analysis

12.1. Statistical Analysis Process

12.1.1. Statistical Analysis Plan

The statistical analysis plan will be discussed and developed jointly by statistical analysts and medical experts. It will be initiated before the end of the study and finalized before database lock. The plan will provide all the content to be covered by the statistical analysis, including the definition of datasets used for analysis, derived algorithms of data, and statistical description and analysis methods adopted for different indicators.

12.1.2. Statistical Analysis Report

Statistical analysis will be strictly conducted according to the requirements of the statistical analysis plan. SAS programs will be prepared using the SAS 9.3 system, debugged, and verified before conducting statistical analysis. Statistical charts and tables that meet the requirements of the statistical analysis plan will be generated. A statistical analysis report will be written based on the generated statistical charts and tables.

12.2. Statistical Analysis Sets

12.2.1. Full Analysis Set (FAS)

The Full Analysis Set (FAS) includes all patients who were enrolled, randomized, and received relevant interventions. Following the principle of Intent-to-Treat (ITT) analysis, patients who did not meet the inclusion criteria, did not receive relevant interventions after randomization, or had no evaluation results should be excluded from this dataset and not included in the statistical analysis. The FAS population is used for non-inferiority evaluation analysis of the primary evaluation indicators.

12.2.2. Per Protocol Set (PPS)

The Per Protocol Set (PPS) includes all cases that comply with the trial protocol, have good compliance, and have completed the required CRF entries. The PPS population is used for non-inferiority evaluation analysis of the primary evaluation indicators and statistical analysis of all secondary evaluation indicators.

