
Specific steps of treatment:

- 1) Apply for a randomization number and obtain the drug number, then quickly open the medicine box. The person opening the box signs the drug list, indicating the date and time of drug administration. Administer intravenous methylprednisolone sodium succinate or placebo, preferably before the establishment of arterial access and no later than 2 hours after the completion of endovascular treatment. The recommended specific dosage of intravenous methylprednisolone sodium succinate or placebo is 2 mg/kg (maximum dose of 160 mg) intravenously once daily, with the first dose administered before surgery for three consecutive days.
- 2) After patients agree to participate and obtain a random number, they will receive intravenous methylprednisolone sodium succinate or placebo as soon as possible, preferably before the establishment of arterial access and no later than 2 hours after the completion of endovascular treatment. Endovascular interventional treatment methods include mechanical thrombectomy, contact aspiration, intraarterial thrombolysis, balloon dilation, and/or emergency stent implantation.

Details of the above treatments must be recorded in detail in the CRF.

Sample Size Calculation and Statistical Methods

1. Sample size calculation

Based on the research results of published literature and combined with clinicians' experience, the 90-day mortality rates of the intravenous methylprednisolone sodium succinate + endovascular treatment group and the placebo + endovascular treatment group were estimated to be 29% and 38%, respectively. The sample size ratio between the two groups was 1:1. Assuming a two-sided α =0.05 and a power of 80%, the estimated sample size was 856 patients. Considering a 5% dropout rate, the maximum estimated sample size was calculated to be 902 patients using PASS 15.0, with 451 patients in each of the intravenous methylprednisolone sodium succinate + endovascular treatment group and the placebo + endovascular treatment group.

2. Statistical analysis

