The intention-to-treat analysis was chosen for statistical analysis of trial efficacy, and the per-protocol dataset (i.e., statistical analysis based on data from all patients who met the trial protocol criteria) was used as a reference. The \times 2 test or Fisher's exact probability method was used to compare event rates, while the t-test or Mann-Whitney U test was used to compare continuous variables. Superiority evaluation indicators were adopted, and statistical tests were performed at a two-sided significance level of 0.05. Differences with $P \leq 0.05$ were considered statistically significant. All statistical analyses were performed using SAS.

3. Programming and analysis of the statistical analysis system.

Trial Schedule	Serial Number	Phases	Start Date	End Date
	1	Preparation	2024-02-01	2024-07-31
	2	Execution	2024-08-01	2025-07-31
	3	Follow-up and Data Collection	2025-08-01	2025-10-31
	4	Data Processing and Analysis	2025-11-01	2025-11-30
	5	Summarizion	2025-12-01	2025-12-31

Table of contents

Lis	t of A	bbreviations	1
Stu	dy Sy	ynopsis	2
1.	Stud	dy Background	3
2.	Stud	dy Objectives	7
3.	Stud	dy Design	7
	Sele 4.1. 4.2. 4.3. 4.4.	tction of Patients, Criteria for Termination and Privacy Protection. 11 Inclusion Criteria 12 Exclusion Criteria 12 Criteria for Termination 12 Privacy Protection 12	1 2 2
5.	Sam	pple Size Calculation	3
	6.1. 6.2.	Randomization	3
	7.1. 7.2. 7.3.	Implementation of Blinding14Emergency Unblinding Procedure14Unblinding Regulations14	4 4
8.	Tre	atment	4
	8.1. 8.2. 8.3. 8.4. 8.5. 8.6.	Treatment Groups	5 5 5 6
9.	Scho	edule of Assessments	6
	9.1. 9.2. 9.3.	Collection of Baseline Data18Randomized Group18Follow-up18	8
10.	End	lpoints of the Clinical Trial	7
	10. 10.	Primary Endpoints	9 9
	10	.2.1. Secondary Efficacy Endpoints	9

The First Affiliated Hospital of Fujian Medical University

11. Adverse Events	. 20
11.1. Definition	. 20
11.1.1. Definition of Adverse Events (AE)	20

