4.4. Privacy Protection

completely stored in the hospital where they receive treatment, and laboratory test reports and other examination results will be recorded in the patients' medical records. Only the investigators, ethics committees, and food and drug administration departments of this study will be allowed to access patients' medical records. Any public reports on the results of this study will not disclose the personal identities of patients. We will make every effort to protect the privacy of patients' personal medical information within the limits allowed by law.

According to medical research ethics, apart from personal privacy information, trial data will be available for public inquiry and sharing. Inquiry and sharing will be limited to web-based electronic databases to ensure that no personal privacy information is leaked.

5. Sample Size Calculation

Based on the research results from published literature and combined with clinicians' experience, the 90-day mortality rates for the intravenous methylprednisolone sodium succinate + endovascular treatment group (experimental group) and the placebo + endovascular treatment group (control group) are estimated to be 29% and 38%, respectively. Assuming a 1:1 ratio for the sample sizes of the two groups, a two-sided α of 0.05, and a power of 80%, the estimated sample size is 856 patients. Considering an expected dropout rate of 5%, the maximum estimated sample size, calculated using PASS 15.0, is 902 patients, with 451 patients in each of the intravenous methylprednisolone sodium succinate + endovascular treatment group (experimental group) and the placebo + endovascular treatment group (control group).

6. Randomization

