12.2.4. Missing Data

12.3. Statistical Analysis Methods

Statistical tests will be performed using a two-sided significance level of 0.05 for indicators evaluated with superiority. Differences with a P-value ≤ 0.05 will be considered statistically significant.

Statistical analysis will be conducted on baseline indicators (such as medical history) and demographic characteristics. Intent-to-treat analysis will be used for statistical analysis of trial efficacy, with the per-protocol dataset (i.e., data from patients who meet all trial protocol criteria) as a reference.

Quantitative data will be described using means, medians, standard deviations, maximum and minimum values, and 25th and 75th percentiles. Comparisons between two groups will be made using the independent t-test or Mann-Whitney U test. Categorical or ordinal data will be described using frequencies and proportions. Comparisons between two groups for categorical data will be made using the chi-square test or Fisher's exact test, and for ordinal data, the Mann-Whitney *U* test will be used.

Previous studies have suggested that the following factors may affect the 90-day mRS score, and this study plans to conduct subgroup analysis based on these variables.

- 1) Age;
- 2) Gender:
- 3) Time of onset;
- 4) NIHSS score:
- 5) ASPECTS score;
- 6) TOAST classification [22];
- 7) Vascular occlusion site;
- 8) Collateral circulation score:
- 9) Anesthesia method:
- 10) Intravenous thrombolysis.

13. Quality Control and Assurance

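### Sections 12.2.1 and 12.2.2 plan a non-inferiority analysis of 90-day mortality with no margin and assign the secondary endpoints to the per-protocol set, against the trial's superiority and ITT basis

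*Combined protocol and SAP*

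**What the plan says.** **Hypothesis.** Section 12.2.1 states: "The FAS population is used for non-inferiority evaluation analysis of the primary evaluation indicators". Section 12.2.2 states: "The PPS population is used for non-inferiority evaluation analysis of the primary evaluation indicators and statistical analysis of all secondary evaluation indicators". Section 10.1.1 makes 90-day mortality the primary efficacy endpoint. The statistical analysis part of the synopsis says instead: "Superiority evaluation indicators were adopted, and statistical tests were performed at a two-sided significance level of 0.05". Section 12.3 sets its testing rule "using a two-sided significance level of 0.05 for indicators evaluated with superiority", but does not say which indicators those are and gives no other kind of test. In the synopsis the 90-day mortality rates on drug and placebo "were estimated to be 29% and 38%, respectively". Section 5 repeats those rates with a two-sided 0.05 level, "and a power of 80%, the estimated sample size is 856 patients", rising to 902 for 5% dropout.

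**Analysis set.** The synopsis says "The intention-to-treat analysis was chosen for statistical analysis of trial efficacy, and the per-protocol dataset" serves as a reference. Section 12.3 repeats the rule: "Intent-to-treat analysis will be used for statistical analysis of trial efficacy, with the per-protocol dataset" again in the reference role. Within section 12.2, the sentence quoted from 12.2.2 is the only one that places the secondary indicators in a set, and the set it names is the PPS. Section 12.2.1 gives the FAS the primary indicators only. Section 12.2.3 sends safety evaluations to the Safety Set.

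**The concern.** The comparator is placebo, and the purpose is to lower mortality. A non-inferiority conclusion would show only that the drug is not worse than placebo by more than some margin. It would not show that the drug saves lives, which is the effect the trial was sized to detect. Without a margin, the analysis named in 12.2.1 and 12.2.2 also cannot be carried out.

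On the analysis set, the PPS selects patients on compliance and completed case report forms. Both are settled after randomisation, so a PPS comparison loses the protection of randomisation. If 12.2.2 is followed literally, all 17 secondary efficacy endpoints in section 10.2.1 are read in that set, although the synopsis and 12.3 give it only a reference role.

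**Working it through.** **1. Which hypothesis does the sample size support?** Inputs from the synopsis and section 5: mortality 29% vs 38%, two-sided alpha 0.05, power 80%, 1:1 allocation, 5% dropout.

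- Unpooled variance: n per arm = (1.96 + 0.8416)² × (0.29×0.71 + 0.38×0.62) / 0.09² = 7.849 × 0.4415 / 0.0081 = 427.8, so 428 per arm and **856** in total. This is the plan's figure.
- Pooled variance gives 430.6, so 431 per arm (862). With continuity correction it is 453 per arm (906).
- Dropout: 428 / 0.95 = 450.5, so 451 per arm and **902** in total. This is also the plan's figure.

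No margin enters. The planned size is that of a two-sided test of zero difference.

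**2. Could 856 be a non-inferiority size?** It cannot be derived as one, because no margin is given. For illustration, with one-sided 0.025 and 80% power:

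| Assumed margin | Total N if true rates are 29% vs 38% | Total N if both are 38% |
|---|---|---|
| 3 points | 482 | 8,220 |
| 5 points | 354 | 2,960 |
| 9 points | 214 | 914 |
| 10 points | 192 | 740 |

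None of these is 856.

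**3. How far apart are the two readings?** Take 428 per arm and observed control mortality of 38%. Let a be observed mortality on the drug, with SE(a) = √[(a(1−a) + 0.38×0.62)/428].

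- Superiority needs 0.38 − a ≥ 1.96 × SE(a). The limit is a = 0.316, a reduction of about 6.4 points.
- Non-inferiority at margin M needs (a − 0.38) + 1.96 × SE(a) < M.

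If the drug has no effect (true mortality 38% in both arms), SE = √(2×0.38×0.62/428) = 0.0332. The chance of declaring non-inferiority is then Φ(M/SE − 1.96).

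| Criterion | Met with observed drug mortality up to | Chance of being met if the drug has no effect |
|---|---|---|
| Superiority, favourable | 31.6% | 2.5% |
| Non-inferiority, M = 3 points (assumed) | 34.5% | 15% |
| Non-inferiority, M = 5 points (assumed) | 36.5% | 33% |
| Non-inferiority, M = 9 points (assumed; equals the planned effect) | 40.4% | 77% |

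The mortality limits are rounded down. At the 9-point margin the criterion is met even with 40.4 − 38 = 2.4 points more deaths on the drug.

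Example: 36% vs 38% observed. The difference is −2.0 points and SE = 0.0330, so the 95% CI runs from −8.5 to +4.5 points and p = 0.54. Superiority is not shown, yet non-inferiority is met at a 5-point margin.

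**4. Analysis set, side by side.**

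| Place | Main efficacy set | Role of per-protocol data |
|---|---|---|
| Synopsis | ITT | Reference |
| 12.3 | ITT | Reference |
| 12.2.1 | FAS, primary indicators only | – |
| 12.2.2 | – | Primary indicators, and all secondary indicators |

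The documents give no expected PPS exclusion rate, so no size is put on the effect for the secondary endpoints.

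**The case against.** The strongest reply is that this is leftover template wording. Every part that sets the design points to superiority: the synopsis says so, the sample size is built that way, and 12.3 offers only ordinary two-sided tests of difference. The SAP must be finalised before database lock and must define the datasets (12.1.1), the analysts are blinded (section 7), and the first unblinding comes after lock and reveals only A/B codes (7.3). On the analysis set, 12.2.2 says what the PPS is used for, without calling it the main or only set, and the general ITT rule in 12.3 can be read as covering secondary efficacy. The margins above are assumptions, and the 77% depends on a margin as large as the whole planned effect.

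Much of this stands. Template residue is the likely cause, the safeguards limit the practical risk, and the margin figures show how far the two readings can diverge rather than measuring an error the trial will make. A supportive reading of 12.2.2 is possible, but then section 12.2 names no main set for the secondary efficacy endpoints.

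The reply does not remove the conflict. The non-inferiority wording appears twice, in the sections that define the sets for the primary endpoint. Nothing says which section prevails, and 12.3 does not name mortality as a superiority indicator. The SAP due before lock is not in the supplied text, and its authors would start from conflicting instructions.

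The plural in both sentences may also take in symptomatic intracranial haemorrhage, listed under section 10.1 as the primary safety endpoint. Mortality is included on either reading, and 12.2.3 already gives safety its own set.

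**Conclusion.** The concern holds and must be fixed. Sections 12.2.1 and 12.2.2 contradict the superiority basis of the synopsis and the sample size, and 12.2.2 conflicts with the ITT-first rule in the synopsis and 12.3. That 856 and 902 reproduce exactly with no margin settles which hypothesis the trial was sized for.

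The size of the divergence depends on the margin. At assumed margins of 3 to 9 points, an ineffective drug would be declared non-inferior about 15% to 77% of the time, against 2.5% for a favourable superiority result. These figures assume 428 evaluable patients per arm, 38% control mortality and the normal approximation. The textual contradiction depends on none of them.

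Some passages were removed from the supplied text. By the table of contents they hold committees, responsibilities, the signature page, appendices and the start of the references, so a margin there is unlikely.

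**What to change.** 1. In 12.2.1 and 12.2.2, replace the non-inferiority wording with a superiority analysis of 90-day mortality at two-sided 0.05.
2. In 12.2, state that the primary and all secondary efficacy endpoints are analysed mainly in the ITT set, with the PPS as supportive only. Safety endpoints, including symptomatic intracranial haemorrhage, stay with the Safety Set under 12.2.3.
3. In 12.3, name 90-day mortality as an indicator evaluated for superiority.
4. Linked point: section 12.2 defines no true ITT set. The FAS in 12.2.1 drops ineligible, untreated and unevaluated patients, and 7.2 removes emergency-unblinded cases from efficacy. Reconcile both with an ITT set of all randomised patients as assigned, and add a missing-outcome rule (12.2.4 shows only its heading in the supplied text).

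The cost is protocol and SAP wording before database lock. The sample size stays at 856 evaluable and 902 randomised, and no new data are collected.

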12.2.3. Safety Set

All patients who have undergone relevant procedures for this trial and have evaluation records are included in this analysis set. Safety and stability evaluations are based on this analysis set.

12.2.4. Missing Data

12.3. Statistical Analysis Methods

Statistical tests will be performed using a two-sided significance level of 0.05 for indicators evaluated with superiority. Differences with a P-value ≤ 0.05 will be considered statistically significant.

Statistical analysis will be conducted on baseline indicators (such as medical history) and demographic characteristics. Intent-to-treat analysis will be used for statistical analysis of trial efficacy, with the per-protocol dataset (i.e., data from patients who meet all trial protocol criteria) as a reference.

Quantitative data will be described using means, medians, standard deviations, maximum and minimum values, and 25th and 75th percentiles. Comparisons between two groups will be made using the independent t-test or Mann-Whitney U test. Categorical or ordinal data will be described using frequencies and proportions. Comparisons between two groups for categorical data will be made using the chi-square test or Fisher's exact test, and for ordinal data, the Mann-Whitney *U* test will be used.

Previous studies have suggested that the following factors may affect the 90-day mRS score, and this study plans to conduct subgroup analysis based on these variables.

- 1) Age;
- 2) Gender:
- 3) Time of onset;
- 4) NIHSS score:
- 5) ASPECTS score;
- 6) TOAST classification [22];
- 7) Vascular occlusion site;
- 8) Collateral circulation score:
- 9) Anesthesia method:
- 10) Intravenous thrombolysis.

13. Quality Control and Assurance

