10.1. Primary Endpoints

10.1.1. Primary Efficacy Endpoint

Mortality at 90±7 days.

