10.2. Secondary Endpoints

10.2.1. Secondary Efficacy Endpoints

- 1) mRS score improvement at 90 ±7 days;
- 2) Proportion of patients with mRS score 0 to 4 at 90 ± 7 days;
- 3) Proportion of patients with mRS score 0 to 3 at 90 \pm 7 days;
- 4) Proportion of patients with mRS score 0 to 2 at 90 ± 7 days;
- 5) Proportion of patients with mRS score 0 to 1 at 90 \pm 7 days;
- 6) mRS score improvement at 1 year;
- 7) Proportion of patients with mRS score 0 to 2 at 1 year;
- 8) Proportion of patients with mRS score 0 to 1 at 1 year;
- 9) mRS score improvement at 5 years;
- 10) Proportion of patients with mRS score 0 to 2 at 5 years;
- 11) Proportion of patients with mRS score 0 to 1 at 5 years;
- 12) NIHSS score at 5-7 days or at early discharge;
- 13) Health-related quality of life [European Quality of Life Five-Dimension visual-analogue scale (EQ-5D VAS)] at 90 ± 7 days;
- 14) Proportion of patients with malignant cerebral edema within 48 hours after EVT
- 15) Proportion of patients with secondary decompressive craniectomy
- 16) EQ-5D VAS at 1 year
- 17) EQ-5D VAS at 5 years

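### The P ≤ 0.05 significance rule is not limited to 90-day mortality, so the secondary efficacy endpoints can yield uncontrolled significance claims

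*Combined protocol and SAP*

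**What the plan says.** - **Rule.** Section 12.3: "Statistical tests will be performed using a two-sided significance level of 0.05 for indicators evaluated with superiority", followed by "Differences with a P-value ≤ 0.05 will be considered statistically significant". The synopsis, under statistical analysis, has the same rule: "Superiority evaluation indicators were adopted, and statistical tests were performed at a two-sided significance level of 0.05". Neither place separates primary from secondary endpoints.
- **Primary.** Section 10.1.1 names one primary efficacy endpoint: "Mortality at 90±7 days".
- **Secondaries.** Section 10.2.1 runs to "17) EQ-5D VAS at 5 years". Items 1-5 all read the same 90-day mRS: the shift and four cut points, for example "Proportion of patients with mRS score 0 to 4 at 90 ± 7 days". Items 6-11, 16 and 17 are at 1 or 5 years.
- **Analysis.** Section 12.2.2 assigns the per-protocol set to "statistical analysis of all secondary evaluation indicators", so all of them are due for analysis.
- **What is absent.** No section supplied gives a testing order, a gate behind mortality, an alpha split or a multiplicity adjustment, and none calls the secondaries supportive or exploratory. The numbering in 10.2.1 is not described as a sequence. Section 12.1.1 leaves detail to a later analysis plan; multiplicity is not among the contents it lists.

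**The concern.** A 5% level controls the error of one test. Here one rule labels every superiority difference at or below 0.05 as significant, whichever endpoint produced it. If mortality turns out null, function is the natural next place to look for a benefit. The plan offers five ways to find one on the 90-day mRS alone and names none of them in advance as the one that counts. A reader of the final report could not tell a pre-specified functional finding from the cut point that happened to cross the line.

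**Working it through.** **1. The plan's own figure.** Section 5 gives 29% against 38%, two-sided 0.05, 80% power and 1:1 allocation. With unpooled variance:

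n per arm = (1.960 + 0.842)² × (0.29×0.71 + 0.38×0.62) / 0.09² = 7.849 × 0.4415 / 0.0081 = 427.8, so 428 per arm and 856 in total.

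With 5% dropout, 428 / 0.95 = 450.5, so 451 per arm and 902 in total. Both figures reproduce, and both use the whole 0.05 on mortality.

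**2. Which secondaries are at stake at the scheduled analysis.** Section 16 ends follow-up on 2025-10-31 and analysis on 2025-11-30. Table 1 in section 9 has no visit after day 90. The eight endpoints at 1 and 5 years (items 6-11, 16, 17) therefore fall outside that analysis. Nine remain: items 1-5 and 12-15. Item 15 (craniectomy) has no time window in the plan and is counted here as due by day 90.

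**3. Reference values if the endpoints were independent.**

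- One two-sided test: 5% in either direction, 2.5% favouring treatment.
- Nine tests, either direction: 1 − 0.95⁹ = 37%.
- Nine tests, favouring treatment: 1 − 0.975⁹ = 20%.
- Five tests, either direction: 1 − 0.95⁵ = 23%.

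The endpoints are not independent. The mRS readings are nested and include death as grade 6, so the true values are lower.

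**4. Simulation with correlated endpoints and no effect on any of them.** The following inputs are assumptions, not document figures, except that 451 per arm is the plan's number and the 38% death share matches its control rate.

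- mRS 0 to 6: 4/7/10/13/14/14/38%.
- Latent correlation of the mRS with NIHSS, EQ-5D VAS, malignant edema and craniectomy: 0.4 to 0.7.
- Edema 30%, craniectomy 10%.
- Tests as in section 12.3: chi-square for proportions, Mann-Whitney for the shift and the scores.

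| Event under no effect | Nine secondaries by day 90 | Five 90-day mRS readings |
|---|---|---|
| At least one P ≤ 0.05, either direction | about 26-30% | about 15% |
| At least one favouring treatment, given non-significant mortality | about 12-14% | about 6% |

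The range for the nine comes from varying the correlations. The five mRS readings depend only on the assumed mRS distribution.

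**5. Size against one test.** 12/2.5 = 4.8 and 14/2.5 = 5.6, so roughly five times the rate of a single test for the nine. For the five mRS readings, 6/2.5 = 2.4 times. The 2.5% is the unconditional rate for one test. Section 12.3 also plans subgroup analyses on ten factors; these are not counted.

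**The case against.** The strongest reply is that one primary endpoint needs no adjustment, that calling the rest secondary already ranks them below mortality, and that unadjusted secondaries read as supportive are a common convention. Much of this stands. Mortality has the full 0.05, and nothing done with the secondaries inflates it. But the plan never says the secondaries are supportive; it gives them the same significance label as the primary.

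A second reply is that the later analysis plan in section 12.1.1 may settle the matter. It may, but the protocol does not commit to that.

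Several stronger readings are tempting, and the documents do not support them:

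- **That the trial's primary error rate is compromised.** It is not.
- **That the false-claim rate is 1 − 0.95¹⁷ = 58%, or about 40% with correlation.** Those figures take in the eight endpoints that mature after the scheduled analysis, and the 58% also assumes independence.
- **That 26-30% is the chance of a false functional benefit.** It includes results favouring placebo and endpoints that are not functional, such as edema and craniectomy. For the 90-day mRS after null mortality, the figure is about 6%.
- **That every comparison in the trial is covered.** Section 12.3 speaks of indicators evaluated for superiority, while sections 12.2.1 and 12.2.2 speak of non-inferiority for the primary indicators. The synopsis says superiority indicators were adopted, so the secondaries are within the rule, but the rule is not universal.
- **That the sponsor plans to claim efficacy on a secondary.** No section says so; the plan simply does not prevent it.

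**Conclusion.** The point holds, confined to claims on secondary efficacy endpoints. As written, the rule gives an uncontrolled significance label to nine secondaries at the scheduled analysis, and nothing in the plan says how such a label is to be read when mortality is not significant. The inflation is material across the nine and modest for the mRS readings alone, because these overlap heavily. The exact percentages depend on the assumed mRS distribution, correlations and event rates. The direction does not: any set of several imperfectly correlated tests at 0.05 exceeds the rate of one. This should be corrected before database lock, but it does not threaten the primary result.

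**What to change.** In section 12.3 and the synopsis, limit the statement of statistical significance for efficacy to 90-day mortality. Add that secondary efficacy endpoints are supportive and will be reported as estimates with 95% confidence intervals and no significance claim. Carry the same wording into the later analysis plan.

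Optionally, if the sponsor wants a confirmatory functional claim, test the 90-day mRS shift at 0.05 only if mortality is significant, with the four cut points as description of the shift. That order keeps the error across the two tests at 0.05.

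Confine the change to efficacy endpoints. The primary safety endpoint, SICH within 48 hours (section 10.1.2), is outside it.

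The cost is a few sentences and the loss of a stand-alone significance claim on an individual secondary efficacy endpoint. Mortality keeps its full two-sided 0.05, so 856 and 902 are unchanged.
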